1.2 Risks and benefits

- **Possible risk:**

A longer treatment time in the open face mask or mask-less phase

- **Possible benefit:**

-Possibly less claustrophobia in the open face mask or mask-less phase

2. Overall study design

The study is designed to evaluate whether irradiating head and neck cancer patients without a mask or with open face masks using SS is comparable to irradiation with full thermoplastic masks in terms of set-up and treatment accuracy and average treatment time.

In total, 24 patients will participate in the study. They are treated with radiotherapy for 35 fractions.

The treatment of every patient will be divided into different phases:

- patients will be irradiated with an open face mask and SS
- patients will be irradiated without a mask but with SS
- patients will be irradiated with a full thermoplastic mask

The delivery technique will change for every patient each 5 fractions.

- The first 8 patients included in the study will have the following schedule:
full mask-open mask-no mask- full mask-open mask-no mask-full mask
- The 9th till 16th patient included in the study will have the following schedule:
open mask-no mask-full mask-open mask-no mask-full mask-open mask
- The 17th till 24th patient included in the study will have the following schedule:
no mask-full mask-open mask- no mask- full mask-open mask-no mask

We chose the number of patients for each group based on the published literature and the power calculation (Table 1).

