7.1 Time and events schedule

The procedures and assessment to be performed throughout the study are outlined in the time and events schedule.

Table 2. Time and events schedule for all participants

Procedure or assessment		Screening	During treatment
Informed consent procedure		x	
Eligibility criteria assessment		x	
ECOG Performance Status		x	
RTT appreciation 0-100			Q1wk
Dutch Claustrophobia questionnaire	Appendix 1	x	
Level of distress	Appendix 2		Q1wk
Treatment time			Every treatment session
In vivo dosimetry			Every first 3 sessions of every phase
Evaluation of the intrafractional motion			Every first 3 sessions of every phase

Abbreviations: Q1wk: weekly

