10.1 Justification of sample size

A sample size of 24 patients was estimated to provide 95% power in order to rule out an excess of 2 mm in mean displacement, assuming a significance level of 0.05 (1-sided as testing for non-inferiority).

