10.2 Statistical plan

A sample size of 24 patients was estimated to provide 95% power in order to rule out an excess of 2 mm in mean displacement, assuming a significance level of 0.05 (1-sided as testing for non-inferiority).

Mean displacements and standard deviations will be compared for the different delivery techniques for each patient. Using the method described by van Herk, population mean displacement (MD), systematic (R) and random (r) errors were estimated.

CBCT registration results will be analysed in 3-dimensions for each patient; population MD, R and r will be calculated. Paired t- tests will be used to compare the parameters listed above, and timing data (CT and treatment session times).

Patient comfort and acceptability questionnaires will be summarised as patient comfort scores ranging from 0 (most comfortable) to 100 (least comfortable).

RTT satisfaction questionnaires will be summarised as scores ranging from 0 (most satisfactory) to 100 (least satisfactory).

Statistical analyses will be performed using SPSS Statistics.

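### Section 10.2 plans paired t-tests on population R, which is one number per technique and cannot be paired; if R is an uncorrected SD of patient means, it also picks up random error

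*Combined protocol and SAP*

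**What the plan says.** Section 10.2 (Statistical plan), repeated almost word for word in the synopsis, compares means and standard deviations of displacement between techniques for each patient. It then moves to population quantities, obtained by the van Herk method: "population mean displacement (MD), systematic (R) and random (r) errors were estimated". CBCT registration results are to be handled in three dimensions, with population MD, R and r calculated. The planned test follows directly: "Paired t- tests will be used to compare the parameters listed above". No formula for R or r is given, and no adjustment for the number of sessions is mentioned.

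The number of sessions is limited by the schedule in section 7.1, where in-vivo dosimetry and intrafractional motion are both assessed at "Every first 3 sessions of every phase". On course length, section 2 says "They are treated with radiotherapy for 35 fractions". On phase length it says "The delivery technique will change for every patient each 5 fractions".

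The sample size in section 10.1 concerns a different quantity: "A sample size of 24 patients was estimated to provide 95% power in order to rule out an excess of 2 mm in mean displacement", at one-sided 0.05 for non-inferiority.

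**The concern.** There are two separate issues.

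- **The test.** A paired t-test needs one value per patient under each technique. A patient has a mean displacement and a session-to-session SD under each technique, so MD and r have patient-level counterparts. R describes the spread between patients and has none. Taken literally, section 10.2 lists R among the compared parameters with a test that cannot be run on it.
- **The estimate.** A patient's mean over a few sessions is not the patient's true systematic displacement, because it still carries random error. If R is the SD of those means with nothing subtracted, part of r is counted in R. The excess depends on each technique's own r, and r is one of the things that may change when the mask is opened or removed.

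The stated aim is to compare accuracy and reproducibility across immobilisation techniques. At stake is whether a difference in random motion gets reported as a difference in systematic error, and whether any difference in R comes with a valid measure of uncertainty.

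**Working it through.** **The plan's own figure.** The only quantitative design figure is 24 patients for 95% power against a 2 mm margin at one-sided 0.05. No SD is given, so it cannot be reproduced. It can only be inverted: SD of paired differences = 2 × √24 / (1.645 + 1.645) = 2.98 mm (normal), or 2.89 mm with the t distribution. It concerns mean displacement, so it does not bear on R.

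**Is a paired test on R possible?**

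| Parameter | Values per technique | Patient-level counterpart | Paired t-test possible? |
|---|---|---|---|
| MD | 1 (population) | the patient's mean | yes, on the counterpart |
| r | 1 (population) | the patient's SD over sessions | yes, on the counterpart |
| R | 1 (population) | none | no |

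This result needs no assumed value and no particular formula.

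**Sessions per patient.** 35 fractions / 5 per phase = 7 phases, each with 3 imaged sessions. From the three sequences in sections 2 and 5, every patient has three phases of one technique (3 × 3 = 9 sessions) and two of each other technique (2 × 3 = 6). Over the three groups of 8, every technique has 8 patients with 9 sessions and 16 with 6:

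mean(1/n) = (16/6 + 8/9) / 24 = 0.148.

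This assumes that everyone completes all 35 fractions. Section 4.3 does not replace patients who withdraw.

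**Size of the excess, if R is the uncorrected SD of patient means.** With sessions independent, expected square = R² + r² × mean(1/n). The documents give no values for R or r, so all of those below are assumptions.

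| True R (mm) | r (mm) | √(R² + 0.148 r²) (mm) |
|---|---|---|
| 1 | 0.5 | 1.02 |
| 1 | 1 | 1.07 |
| 1 | 1.5 | 1.15 |
| 1 | 2 | 1.26 |
| 1 | 3 | 1.53 |
| 0.5 | 1 | 0.63 |
| 0.5 | 2 | 0.92 |

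The inflation is therefore about 2% at r/R = 0.5, 7% at 1 and 26% at 2.

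**How often this changes the ranking.** In simulation (24 patients, the session counts above, 20,000 runs, equal true R), the noisier technique should show the larger R in 50% of trials.

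- True R = 1 mm: 59% for r = 0.5 against 1, 64% for 1 against 1.5, 78% for 1 against 2, and 95% for 1 against 3.
- True R = 0.5 mm: 96% for r = 1 against 2.

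Subtracting 0.148 r² brings the 78% case to 49%.

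**Correlation within a phase.** Sessions in the same phase may resemble each other. Take an assumed correlation of 0.3, true R = 1 mm and r = 2 mm:

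- phase variance = 0.3 × 4 = 1.2 and session variance = 2.8;
- a phase mean over 3 sessions has variance 1.2 + 2.8/3 = 2.133;
- mean(1/phases) = (1/3 + 1/2 + 1/2)/3 = 0.444;
- expected square = 1 + 0.444 × 2.133 = 1.948, root 1.40 mm.

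For r = 1 the same steps give 1 + 0.444 × (0.3 + 0.7/3) = 1.237, root 1.11 mm. The simple subtraction leaves 1.05 against 1.19 mm in simulation. A phase-within-patient term removes the whole 0.444 × 2.133 component and so returns 1 mm in expectation.

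**The case against.** The strongest reply is that the documents do not say R is an uncorrected SD of patient means. They name a method without printing it, and whether that method adjusts for few sessions cannot be checked here. This stands: the bias is conditional, and printing the formula could dispose of it. The paired-test problem would remain.

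A reader might go further and infer that the no-mask technique will falsely show a larger systematic error. The documents do not support that. They give no values for R or r and no evidence that r differs between techniques. The effect is a bias in expectation. At r = R = 1 mm it is 0.07 mm against a sampling SD of R of about 0.16 mm, and correcting it leaves the root-mean-square error at about 0.17 mm either way. If true systematic errors differ in the other direction, the order need not reverse.

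Nor do the documents support the inference that the powered comparison is compromised. Sample size and non-inferiority rest on mean displacement, which this mechanism does not bias.

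One can also say that r is reported beside R, so a reader would see the noisier technique. That is fair, and an overall conclusion of poorer reproducibility would be right. The split between systematic and random error would still be wrong, and the plan sets out to estimate each.

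Equal session counts are a weaker defence. They stop the counts themselves from favouring a technique if everyone completes, but the excess follows each technique's own r² and cancels only if r is equal.

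Finally, the t-test wording also covers per-patient means and SDs, where pairing is valid. True, but it does not exclude R and offers nothing else for it.

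**Conclusion.** The point holds in two parts of different strength. The firm part is that section 10.2 has no valid test for population R, because R is one number per technique. This follows from the text alone.

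The conditional part is that an uncorrected SD of patient means would carry an extra 0.148 r² in its square. R then tends to read higher for a technique with more random motion. For true R = 1 mm, the difference between r = 1 and r = 2 is 1.26 − 1.07 = 0.19 mm (18%), and the effect is negligible when r is half of R. These sizes rest on assumed R and r, independent sessions, and complete follow-up. Within-phase correlation would make them larger.

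Mean displacement and the sample size are untouched. This should be fixed before analysis, but it does not threaten the non-inferiority comparison.

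**What to change.** In section 10.2, and in the matching synopsis text:

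1. Print the formulas for MD, R and r.
2. Limit paired t-tests to patient-level means and patient-level SDs (and the timing data already named).
3. Estimate R and r for each technique by a variance-components model with patient and phase-within-patient random effects. A model with patient as the only random factor is not enough if sessions within a phase correlate.
4. Compare R and r between techniques with a bootstrap confidence interval that resamples patients, keeping each patient's data on all three techniques together.

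The cost is a short edit and a few lines of syntax, with no new imaging, data or patients.

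There is a real downside. With 24 patients the estimate of R² can be zero or negative when r is well above R. At an assumed R = 0.5 mm and r = 2 mm, simple subtraction gives this in about one simulated trial in six, and the truncated R averages 0.44 mm with SD 0.27 mm. Such an estimate should be reported as 0 with its interval. The uncorrected SD of patient means can be shown alongside, labelled as such, for comparison with the literature.

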Participant selection criteria:	
Each potential subject must satisfy all of the following criteria to be enrolled in the study.
 
 - Patients \geq 18 years old - Histologically confirmed head and neck cancer. - Patients treated with RT as primary treatment. - An Eastern Cooperative Oncology Group (ECOG) Performance Status grade of 0-1. - Each subject must sign an informed consent form (ICF) indicating that he understands the purpose of and procedures required for the study and is willing to participate in the study. - Patients must be willing to comply with treatment plan and other study procedures. 
Each potential subject must NOT have any of the following criteria to be enrolled in the study.
 
 - Patients with significantly altered mental status or with psychological, familial, sociological or geographical condition potentially hampering compliance with the study. - Individual deprived of liberty or placed under guardianship. - Patients who cannot stay still during fraction because of a disorder (e.g. Parkinson's disease)
Treatment:	
The treatment of every patient will be divided into different phases:
 
 -patients will be irradiated with an open face mask and SS -patients will be irradiated with SS without a mask -patients will be irradiated with a full thermoplastic mask 
The delivery technique will change for every patient each 5 fractions. The first 8 patients included in the study will have the following schedule: full mask-open mask-no mask-full mask-...
 
The 9th till 16th patient included in the study will have the following schedule: open mask-no mask-full mask-open mask-...
 
The 17th till 24th patient included in the study will have the following schedule: no mask-full mask-open mask-no mask-...

Duration of study:	12 months
Accuracy:	
 - In-vivo dosimetry using PerFRACTION - Evaluation of intrafractional motion by comparing a CBCT before and at the end of treatment
Statistical methods:	A sample size of 24 patients is estimated to provide 95% power in order to rule out an mean displacement in excess of 2 mm, assuming a significance level of 0.05 (1-sided as testing for non-inferiority).

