3.1 Primary objective

We would like to investigate whether irradiation with open face masks and SS, and without masks and SS, for patients with head and neck cancer is at least as good as irradiation with a full thermoplastic mask in terms of set-up and treatment accuracy.

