7.2 Study procedures

The study procedures are described in subsequent sections

Patient demographics and other screening characteristics

The data that will be collected at screening include:

- Demography (date of birth)
- ECOG performance status (Appendix 3)
- Patient questionnaire: the Dutch Claustrophobia questionnaire
- Use of anxiolytic medication

Accuracy assessments

- using PerFRACTION (in vivo dosimetry)
- using the intrafractional motion determined by the change in position between the CBCT pre and post treatment

Assessment of patients' distress level

-Weekly using the level of distress (see appendix)

Assessment of treatment time

-Will be done automatically using the radiotherapy delivery software

Assessment of RTT preference

- Using score of 0-100

8. Safety monitoring and reporting

ICH GCP and the EU Directive 2001/20/EC require that both investigators and sponsors follow specific procedures when notifying and reporting adverse events/reactions in clinical trials. These procedures are described in this section of the protocol.

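### Section 10.2 states a 2 mm non-inferiority aim but does not tie its paired t-tests to that margin or say which displacement is tested, and the synopsis words the margin differently

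*Combined protocol and SAP*

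**What the plan says.** Section 3.1 asks whether open mask with surface scanning, and no mask with surface scanning, "is at least as good as irradiation with a full thermoplastic mask in terms of set-up and treatment accuracy". Sections 10.1 and 10.2 give 24 patients, 95% power, one-sided 0.05 and non-inferiority, the aim being to "rule out an excess of 2 mm in mean displacement". The synopsis (Statistical methods) instead says "rule out an mean displacement in excess of 2 mm".

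On analysis, section 10.2 says "CBCT registration results will be analysed in 3-dimensions for each patient; population MD, R and r will be calculated", refers to the van Herk method for these quantities, and continues: "Paired t- tests will be used to compare the parameters listed above, and timing data (CT and treatment session times"). The margin does not appear again after the sample-size sentence.

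Section 7.2 gives the source measurement: "using the intrafractional motion determined by the change in position between the CBCT pre and post treatment". Table 2 in section 7.1 sets the sessions measured: "Every first 3 sessions of every phase". Section 2 sets the phases: "The delivery technique will change for every patient each 5 fractions".

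**The concern.** A non-inferiority conclusion needs three things fixed in advance: the quantity compared, the value it is tested against, and the rule for declaring success. Section 10.2 supplies a margin and an alpha for the power statement but does not carry them into the tests.

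- **Null value.** The t-test sentence covers MD, R, r and times together, while a margin exists only for mean displacement. It therefore cannot serve as the non-inferiority rule for everything it lists. If it were applied as an ordinary test against zero, a non-significant result could be taken as equivalence, and a difference well inside 2 mm could be taken as failure.
- **Measure.** MD is reported apart from the systematic error (R) and the random error (r). If MD is a signed mean, motion in opposite directions cancels. MD can then satisfy a 2 mm limit while movement without a mask is much larger. R would show this, but R has no margin.
- **Form of the margin.** A ceiling on displacement and an excess over the full mask are different hypotheses.

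At stake is whether the same data could support different answers on maskless treatment, depending on choices made after the data are seen.

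**Working it through.** **Inputs from the documents:** n = 24, paired (every patient receives all three techniques); margin 2 mm; one-sided alpha 0.05; power 95%. **Not given:** any SD or assumed true difference. All SDs and true means below are therefore assumptions, except the implied SD in step 1, which itself assumes a true difference of 0.

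**1. The plan's own figure.** With no SD stated, 24 cannot be derived forwards, so I solve for the SD of the paired difference that it implies.
- Normal approximation: SD = 2 × √24 / (1.645 + 1.645) = 2.98 mm.
- Paired t (noncentral t, 23 df): 2.89 mm.

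At SD 2.89 mm the margin rule is met if the observed mean difference is below 2 − 1.714 × 2.89/√24 = 0.99 mm. By construction it passes 5% of the time when the true excess is 2 mm.

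**2. Test against zero versus test against the margin.** The two-sided 5% critical value is 2.069, and the noncentrality is (true excess) × √24 / SD. For example, with a 2 mm excess and SD 2.89 mm it is 2 × 4.899/2.889 = 3.39.

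True excess 2 mm:

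| SD (mm) | Zero test non-significant | Margin rule passes |
|---|---|---|
| 2 | 0.3% | 5% |
| 2.5 | 3.7% | 5% |
| 2.89 | 9.9% | 5% |
| 4 | 35% | 5% |

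True excess 0.6 mm:

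| SD (mm) | Zero test significant | Margin rule passes |
|---|---|---|
| 1 | 80% | >99.9% |
| 2 | 29% | 95% |
| 2.89 | 16% | 74% |

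False reassurance is a problem only at the larger SDs. At SD 4 mm, 24 patients would give 77% power, which does not fit the stated 95%. The opposite error, calling a small difference a failure, dominates at small SDs.

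**3. Choice of measure.** Assume normal, zero-mean motion, with systematic and random SD per axis equal: 0.5 mm each with the full mask and s mm each with no mask. The total SD per axis is then s√2, and the mean 3D length is 2√(2/π) × s√2. With the full mask this is 1.596 × 0.707 = 1.13 mm. At s = 1.5 it is 1.596 × 2.121 = 3.39 mm, a true excess of 2.26 mm.

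Pass rates for the rule that the upper one-sided 95% limit is below 2 mm come from 20,000 simulated trials per setting. Sessions per patient follow from the schedule: full mask 9, 6 and 6, and no mask 6, 6 and 9, in the three sequence groups of 8.

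| No-mask SD (mm) | 3D-length excess (mm) | Pass: 3D length | Pass: absolute, one axis | Pass: signed, one axis |
|---|---|---|---|---|
| 1.0 | 1.13 | 100% | 100% | 100% |
| 1.2 | 1.58 | 84% | 100% | 100% |
| 1.3 | 1.80 | 35% | 100% | 100% |
| 1.5 | 2.26 | 0.2% | 99.8% | 100% |

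The measures agree up to a doubling of the SD and diverge beyond it. In these simulations the SD of single-axis patient means, which R reflects, rises from about 0.53 mm (full mask) to between 1.06 and 1.59 mm (no mask), so R would reveal the larger motion.

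**4. Ceiling versus excess (illustration).** Assume means of 1.5 mm (full mask) and 2.5 mm (no mask), and SD 1 mm both for the difference and for the single-technique value. The excess rule passes 99.9% of the time and the ceiling rule 0.003%. The no-mask mean is set above the ceiling, so this shows only that the two wordings can disagree, not how often they would.

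**The case against.** Much of the rule can be inferred. Section 10.2 itself carries the margin, the one-sided alpha and the word non-inferiority, so a two-sided zero test would contradict its first sentence. Both comparisons with the full mask are set in section 3.1 and in the PICO list under section 3.4. The raw measurement and the measured sessions are given, the results are to be analysed in three dimensions, and the named method may settle sign and axis. These points stand. A reader might infer that a zero test is planned, that displacement is undefined altogether, or that the comparators are missing. The documents support none of these.

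The false-reassurance risk is also modest at SDs that fit the stated power: 9.9% against 5% at 2.89 mm, and below 5% at 2.5 mm or less. In step 3 the signed mean passes because zero-mean motion is assumed.

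The synopsis may simply be loose English, since its sentence also ends in non-inferiority, which implies a comparator.

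What remains is that no sentence links the tests to 2 mm, and the documents' own text does not state sign, axis or vector length for mean displacement. The source for the named method is not in the reference list, so it cannot be relied on to fill that gap.

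**Conclusion.** The point holds as a gap in specification that should be fixed. The reading closest to the text is a one-sided test against 2 mm, but it is not written down, and the choice of measure stays open even under that reading.

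The effect of the null value is moderate at the implied SD (9.9% against 5%). At an assumed SD of 1 mm, a true 0.6 mm excess would be flagged as a difference 80% of the time although non-inferiority would almost always be shown. The effect of the measure can be decisive: 100% against 0.2% when the assumed no-mask SD is three times the full-mask SD, but nil up to a doubling. The implied SD assumes a true difference of 0, and the measure result assumes normal, zero-mean motion.

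A reader might also infer that the sample size is wrong. The documents do not allow that conclusion: 24 fits a paired SD of about 2.9 mm, and no SD is given against which to judge it. The synopsis wording is a secondary matter of alignment.

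**What to change.** 1. **Synopsis:** word the margin as in sections 10.1 and 10.2, stated explicitly as a difference from the full mask.
2. **Section 10.2, measure:** fix one measure in advance, namely each patient's mean 3D vector length of the pre- to post-treatment CBCT displacement for each technique. State that the 2 mm margin applies to that measure. Report per-axis values, R and r beside it. Leaving a choice between vector length and per-axis absolute displacement would not close the gap, because step 3 shows that they can give opposite answers under the same margin.
3. **Section 10.2, rule:** add: *For each of open mask vs full mask and no mask vs full mask, non-inferiority is concluded separately if the upper one-sided 95% confidence limit of the mean within-patient difference (technique minus full mask) is below 2 mm.*
4. **Section 10.2, other quantities:** state that R, r and times are descriptive, and that a non-significant difference from zero is not evidence of non-inferiority. R is presented as a population quantity, so it offers no patient-level pairs for a paired t-test.

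This rule covers displacement only. In-vivo dosimetry and treatment time, also listed in section 3.2, have no stated margin and are not settled by it.

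The cost is wording in the synopsis and section 10.2, with no extra patients or data. It should be done before the displacement data are analysed.

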1.1 Background & rationale

Head and neck cancer (HNC) is a broad term that encompasses a large number of tumour entities originating from different subsites, such as the nasal cavity, nasopharynx, oral cavity, oropharynx, larynx, hypopharynx and salivary glands.

In Belgium, in the year 2016 (latest data Belgian Cancer Registry), more than 2500 patients were diagnosed with head and neck cancer. (1) In the United States, for the year 2014, there was an estimate of 55.070 new cases of HNC (2). Approximately 60% to 80% of HNC patients present with loco-regionally advanced disease at time of diagnosis. The main treatment options for loco-regionally advanced HNC are (chemo-) radiotherapy (RT) and surgery (often followed by RT). During each RT course, patients are immobilised using a thermoplastic mask (**Figure 1 a.**) to limit the possibility to move during the treatment. Furthermore, this mask enables correct positioning before the start of each RT session.

[figure not shown]

Figure 1. Full thermoplastic mask (a.) and open thermoplastic mask (b.).

The use of these masks results in the following disadvantages:

- They can cause claustrophobia and anxiety. (3, 4, 6)
- Intrafractional surface monitoring is not possible with closed masks. (3)
- Full-face masks can be very uncomfortable and cause pain by pressure. (5, 6, 7)
- The masks don't adapt to weight loss or edema that can occur during radiotherapy.

Lately, to reduce these side effects, there is an interest in using open face masks (**Figure 1 b.**) in combination with surface scanning (SS). SS is a system which tracks a patient's position before and during RT, to aid in setup and treatment accuracy. Using 3D stereo camera units, the SS tracks the skin surface, and compares it to the ideal position. (4) The combination of an SS and an open face mask therefore enables us to monitor intrafractional movement. (8) This system can then automatically signal the treatment delivery system to pause radiation if the patient moves out of the desired position.

The use of SS together with open face masks for HNC has been studied. An overview of the relevant literature review can be found in **Table 1**.

Article	Number of participants	Hypothesis	Conclusion

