4.3 Subject withdrawal criteria and procedures

- The general condition of the patient is too bad to continue the RT
- The patient can withdraw from the study at any moment for any reason

The patients who withdraw will not be replaced.

Specific aftercare for this therapeutic strategy is no different from the current standard of care.

5. Treatment allocation

Patients will be assigned to a study group based on their date of enrolment.

The treatment of every patient will be divided into different phases:

- patients will be irradiated with an open face mask and SS
- patients will be irradiated without a mask but with SS
- patients will be irradiated with a full thermoplastic mask

The delivery technique will change for every patient each 5 fractions.

[figure not shown]
- The first 8 patients included in the study will have the following schedule:
full mask-open mask-no mask- full mask-open mask-no mask-full mask
- The 9th till 16th patient included in the study will have the following schedule:
open mask-no mask-full mask-open mask-no mask-full mask-open mask
- The 17th till 24th patient included in the study will have the following schedule:
no mask-full mask-open mask- no mask- full mask-open mask-no mask

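### The plain paired t-tests in section 10.2 ignore the three schedules: a phase effect common to all techniques would make them conservative, and uneven withdrawals would add a small bias

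*Combined protocol and SAP*

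**What the plan says.** All references are to the combined protocol and SAP.

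- **Analysis (section 10.2):** "Paired t- tests will be used to compare the parameters listed above, and timing data (CT and treatment session times". The parameters meant are the displacement measures. No sequence, phase or enrolment-block term is named.
- **Design (sections 2 and 5):** 35 fractions, and "The delivery technique will change for every patient each 5 fractions", which gives seven phases. Patients 1 to 8 follow "full mask-open mask-no mask- full mask-open mask-no mask-full mask", patients 9 to 16 "open mask-no mask-full mask-open mask-no mask-full mask-open mask" and patients 17 to 24 "no mask-full mask-open mask- no mask- full mask-open mask-no mask". Groups are filled in order of enrolment.
- **Withdrawals (section 4.3):** patients who leave are not replaced.
- **Power (section 10.1):** "A sample size of 24 patients was estimated to provide 95% power in order to rule out an excess of 2 mm in mean displacement". The comparison is a one-sided non-inferiority test at the 5% level. No SD and no assumed true difference are given.
- **Endpoints (section 3.2):** average treatment time is listed under the primary endpoint next to accuracy, and section 10.2 names timing for the paired test.

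**The concern.** Three techniques do not divide evenly into seven phases, so in no patient do all three techniques share the same mean phase. If motion or session time changes over the course in a way common to all techniques, each patient's paired difference picks up a shift fixed by the schedule. A paired t-test on 24 differences cannot tell that known shift from random variation. At stake is some precision in the non-inferiority comparison and the timing comparison. If the three groups end up unequal, or patients stop part-way, a small bias is added. The phase structure is known for every patient, so it can be allowed for without new data.

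**Working it through.** **Reproducing the power figure.** The 95% cannot be checked directly because no SD is stated. If the true difference is 0, the paired-difference SD that gives 95% power is, by the normal formula, 2 × √24 / (1.645 + 1.645) = 2.98 mm, and by the noncentral t with 23 df, 2.89 mm. I use 2.89 mm as the value anchored in the documents, and 1 mm as an assumed low value.

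**Mean phases.** These come from the written sequences, with each patient's technique value taken as the mean over its phases (an assumption, as the plan does not say).

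| Group | Full | Open | None | Open − full | None − full |
|---|---|---|---|---|---|
| 1 | 4.0 | 3.5 | 4.5 | −0.5 | +0.5 |
| 2 | 4.5 | 4.0 | 3.5 | −0.5 | −1.0 |
| 3 | 3.5 | 4.5 | 4.0 | +1.0 | +0.5 |

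Each of the last two columns sums to 0. With 8/8/8 completers, a common linear trend b per phase therefore leaves no bias.

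**Added variance.**
- Linear trend: (0.25 + 0.25 + 1.0)/3 = 0.5, so 0.5b².
- First-phase effect h: the technique used first has three phases, so its mean rises by h/3. Open − full shifts by −h/3, +h/3 and 0 in groups 1 to 3. The variance is (2/9)/3 = 0.074, so 0.074h². None − full has the same variance.

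The sample variance carries the factor 24/23, so the SE ratio is √(1 + V × 24/23 / SD²), where V is the added variance.

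**Interval half-width, unadjusted (t 1.714, 23 df) against sequence-adjusted (t 1.721, 21 df).** Trends and SDs are assumptions.

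| SD | b per phase | Unadjusted | Adjusted | Ratio |
|---|---|---|---|---|
| 2.89 mm | 0.2 mm | 1.012 mm | 1.015 mm | 0.997 |
| 2.89 mm | 0.5 mm | 1.018 mm | 1.015 mm | 1.004 |
| 2.89 mm | 1.0 mm | 1.042 mm | 1.015 mm | 1.027 |
| 1.0 mm | 0.5 mm | 0.372 mm | 0.351 mm | 1.059 |
| 1.0 mm | 1.0 mm | 0.432 mm | 0.351 mm | 1.229 |

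- Session time, h = 5 min, SD 3 min: V = 0.0741 × 25 = 1.852, and √(1 + 1.852 × 24/23 / 9) = 1.102. The SE is about 10% larger.
- Break-even: b/SD = √[((1.7207/1.7139)² − 1) × 23/24 / 0.5] = 0.124 per phase, or 0.36 mm per phase at SD 2.89 mm. Below this, the adjusted interval is the wider one.
- Validity: in 40,000 simulated trials at SD 1 mm, the one-sided type I error of the plain test was 0.042 at b = 0.5 and 0.021 at b = 1.0, against a nominal 0.05.

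**Unequal groups.** With 8/8/6 completers:
- open − full: (−4 − 4 + 6)/22 = −0.09b
- none − full: (4 − 8 + 3)/22 = −0.05b

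With 8/8/4 these become −0.20b and −0.10b.

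**Stopping mid-course.** A group 1 patient who stops after phase 3 has full, open and none at phases 1, 2 and 3. The shifts are then +1b and +2b, against −0.5b and +0.5b for a completer in that group.

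**The case against.** The strongest reply is that little is lost. The rotation already removes a common trend from the mean, and the plain paired test keeps that benefit. For displacement, the gain at the implied SD is trivial, and at SD 1 mm the power against 2 mm is about 100% with either analysis. The motion endpoint is movement within a session, so 0.5 mm per phase would mean a 3 mm rise from phase 1 to phase 7, against a 2 mm margin. Nothing in the documents points to that. All of this stands.

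Two further limits also stand. The protocol's own reason to expect change, "The masks don't adapt to weight loss or edema that can occur during radiotherapy" (section 1.1), describes a trend specific to masks, which an additive phase term does not represent. Trends that differ between patients stay in the error with or without adjustment.

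A reader might also infer more than the documents support:
- *That the planned standard errors are invalid, or the design's balance is thrown away.* Neither follows. The estimate is unbiased with 8/8/8, and the test errs on the conservative side.
- *That with unequal groups the shifts no longer cancel.* Most of the cancellation remains. At 8/8/6 and b = 0.5 mm the bias is below 0.05 mm.
- *That the distress comparison is affected in the same way.* Section 10.2 only summarises comfort scores and names no test for them.

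**Conclusion.** The point holds as a precision and robustness improvement. It does not make the planned test invalid. Under a phase effect common to all techniques, the plain paired test with 8/8/8 completers is valid but conservative. How much wider its interval is depends on a trend and an SD that the documents do not give: from negligible to under 3% at the SD implied by the power statement, about 6% at SD 1 mm with 0.5 mm per phase, and slightly in the plain test's favour below about 0.12 SD per phase. The displacement conclusion is unlikely to change. The case is strongest for treatment time, where an early-phase effect could plausibly be large relative to the SD, and for uneven or mid-course withdrawal.

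**What to change.** In section 10.2, for mean displacement and treatment time, replace the plain paired t-test by an analysis of each within-patient difference with sequence group (3 levels) as a factor. Report the equally weighted mean of the three group means with its one-sided 95% limit (21 df when all 24 complete). For completers, equal weighting also removes the bias from unequal group sizes under a common phase effect.

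An alternative that also handles incomplete courses is a mixed model on session values, with technique and phase (1 to 7) as fixed effects and patient and patient-by-phase as random effects. It is not identical to the first analysis: weights, degrees of freedom and variance structure differ. The plan should therefore name one as primary.

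The cost is a change of wording, with the same data and the SPSS software already named. The downside is two degrees of freedom (t 1.721 instead of 1.714), which widens the interval by about 0.4% if there is no trend.
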